#### 2.5.3. Third Outcome Measure: Evaluation of Wound Conditions

Diabetic foot ulcers were evaluated at patient admission and weekly before and after each debridement treatment. A validated wound scoring system was used to assess the wound bed tissue according to quality, presence and consistency of granulation tissue [25]. Furthermore, diabetic foot ulcers were evaluated for amounts of wound exudate and periwound skin conditions such as skin maceration by the same senior clinician ([name]) according to the triangle wound assessment [26].

Wound healing was supervised weekly during the treatment period (6 weeks) and the wound size was assessed using Visitrak (Smith & Nephew, Hull, UK), determining the area of the lesion with an approximation of  $\pm 5 \text{ mm}^2$ .

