#### 2.2. Participant

We enrolled patients in which the following inclusion criteria were implemented:

- Male and female patients over 18 years old

Type 1 or type 2 diabetes with levels of HbA1c  $\leq 85.8$  mmol/mol (10%) within 30 days of the beginning of the study, based on a previous international, multicenter, randomized controlled trial [11]

- Wound stages IB, IIB, ID, and IID according to the University of Texas Diabetic Wound Classification [12]
- Wound duration of 1–24 months
- Wound size among 1–30 cm^2 after debridement

- Diabetic foot ulcers showing mild or moderate infection, according to the criteria of the European Wound Management Association (EWMA) [13] and the Infectious Disease Society of America Guidelines [14]
- Ankle-brachial index (ABI)  $> 0.9$  or  $ABI \leq 0.9$  and ankle systolic blood pressure (ASBP)  $\leq 70$  mmHg, or toe systolic blood pressure (TSBP)  $50$  mmHg. In patients with medial arterial calcification (ABI  $> 1.4$ ) we considered Peripheral Arterial Disease (PAD) a toe-brachial index (TBI)  $< 0.7$  [15,16]

We considered exclusion criteria:

- Chronic kidney disease (glomerular filtration rate  $< 60$  mL/min per 1.73 m^2 during at least three months) or dialysis [17]
- Non-treated osteomyelitis
- Necrotizing soft tissue infections
- Critical limb ischemia patients with ABI  $< 0.5$  and ASBP  $< 70$  mmHg or  $< 50$  mmHg [15,16]

Life expectancy  $< 6$  months due to malignant DFU

- Pregnancy and lactation
- Patients diagnosed with human immunodeficiency virus (HIV) or hepatitis
- Patients showing local or systemic conditions that could impair tissue regeneration.

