#### 2.7. Sample Size

Granmov.12 program (Municipal Institute of Medical Research, Barcelona, Spain) (<https://www.imim.cat/ofertadeserveis/software-public/granmo/>) was used to calculate the sample size. Thus, we analyzed 51 patients (24 in surgical group and 27 in UAW group) with a statistical power of 0.80 and an alpha of 0.05, with a

power of the clinical difference of 37% to detect a statistically significant between groups.

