## 2.10. Statistical analysis

Data were analyzed, based upon an intention-to-treat analysis, using the software package SPSS for iOS version 21.0 (SPSS, Inc. Chicago, IL, USA). Kolmogorov-Smirnov test was used to verify the assumption of normality of all continuous variables. Chi-square test was performed to calculate differences between groups and, if applicable, Fisher's exact test for categorical variables. Student's t-test and Mann-Whitney U test were performed for normally and abnormally distributed quantitative variables, respectively. Graphics to evaluate the differences among decrease in bacterial load and cellular proliferation between groups were done using GraphPad® for Mac OS.

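### The wound-size variable is not defined and the only tests named are unadjusted; testing week-6 area or cm² decrease without day-0 area would lose much precision on this third-ranked outcome.

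*Combined protocol and SAP*

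**What the plan says.** Section 2.2 (Participant) sets wide limits on the starting ulcer: "Wound size among 1–30 cm"², taken after debridement, and "Wound duration of 1–24 months".

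Section 2.5.3 (Third Outcome Measure) has ulcers evaluated at admission and each week, before and after debridement. It adds: "Wound healing was supervised weekly during the treatment period (6 weeks) and the wound size was assessed using Visitrak". The area is accurate to about ±5 mm². A starting area should therefore exist for every patient, but the section does not say which quantity derived from these areas is compared between arms.

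Section 2.10 (Statistical analysis) gives this rule for quantitative variables: "Student's t-test and Mann-Whitney U test were performed for normally and abnormally distributed quantitative variables, respectively". It names no covariate, change score, percent reduction or repeated-measures model. The word decrease occurs there only for graphics of bacterial load and cellular proliferation.

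Section 2.8 describes a random number table and mentions no stratification. Section 2.7 states: "we analyzed 51 patients (24 in surgical group and 27 in UAW group").

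**The concern.** Ulcers may differ 30-fold in area on day 0 (30 ÷ 1). Much of the spread in week-6 area may then simply be the spread in starting area. An absolute decrease in cm² carries the same problem, because a large ulcer can lose more cm² than a small one. With 24 and 27 patients, an unadjusted test of either quantity could miss a real difference in shrinkage that an analysis using day-0 area would detect.

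The plan also leaves three candidate variables open, and they differ widely in power. Under section 2.9 outcome adjudicators are not blinded, so the choice should be fixed in writing.

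**Working it through.** **The plan's own figure.** Section 2.7 gives 51 patients "with a statistical power of 0.80 and an alpha of 0.05" and a 37% difference, without naming the endpoint, control rate or SD. I read 37% as a difference in proportions p₂ − p₁ = 0.37, two-sided, with allocation ratio k and no continuity correction:

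n₁ = [1.96·√(p̄(1−p̄)(1+1/k)) + 0.84·√(p₁(1−p₁) + p₂(1−p₂)/k)]² / 0.37²

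Over control rates 0.05 to 0.60 the total is 38 to 56 at k = 1. At k = 27/24 it is 51 for control rates 0.15 and 0.45. So 51 is attainable but cannot be verified, and nothing ties it to wound size.

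**Gain from adjustment, for any scale.** Adjusting for a baseline with correlation ρ leaves a fraction 1 − ρ² of the variance. Unadjusted, the difference detectable at 80% power is (1.96 + 0.84)·√(1/24 + 1/27) = 2.80 × 0.2805 = 0.79 SD. Adjusted, it is 0.79·√(1 − ρ²), and the information equals that of 51/(1 − ρ²) patients.

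| ρ (assumed) | 1 − ρ² | Equivalent N | Detectable difference (SD) |
|---|---|---|---|
| 0.3 | 0.91 | 56 | 0.75 |
| 0.5 | 0.75 | 68 | 0.68 |
| 0.7 | 0.51 | 100 | 0.56 |
| 0.8 | 0.36 | 142 | 0.47 |

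**Worked case.** The patient numbers and area limits come from the plan. The rest is assumed, because the plan gives no SD or correlation:
- SD of log day-0 area about 0.80 (median about 4.4 cm², truncated to 1–30 cm²).
- True effect 0.6 on the log scale, that is 1 − e^(−0.6) = 45% smaller area under UAW.
- SD of individual log healing s = 0.6 to 1.2.

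On the log scale, week-6 area has SD √(0.80² + s²) unadjusted and s after adjustment. Approximate power is Φ(0.6/(SD × 0.2805) − 1.96).

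- s = 0.6: unadjusted SD 1.00, Φ(2.14 − 1.96) = 57%; adjusted Φ(3.57 − 1.96) = 95%.
- s = 1.2: unadjusted SD 1.44, Φ(1.48 − 1.96) = 32%; adjusted Φ(1.78 − 1.96) = 43%.

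Simulations of the actual tests (mostly 2,000 runs per setting, with small differences in the assumed day-0 distribution) agree:

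| s | Mann-Whitney, week-6 area | Mann-Whitney, percent reduction | Log area adjusted for log day-0 area |
|---|---|---|---|
| 0.6 | 50–58% | 91–93% | 92–94% |
| 0.8 | 42–46% | 72% | 72–74% |
| 1.0 | 36–38% | 49–53% | 54–55% |
| 1.2 | 28–32% | 38–41% | 39–43% |

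False-positive rates were 3–6%.

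**Absolute decrease.** Power depends heavily on how much ulcers shrink on average. At s = 0.6 it was about 59% for a common log shrinkage of 0.5 and about 24% for 1.0. No single figure should be quoted, but both lie well below 92%.

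**Smaller effect.** With a true 37% smaller area and day-0 area uniform, log-uniform or log-normal, healing SD 0.5 to 0.8 gives 18–51% for unadjusted week-6 area and 51–90% adjusted. At SD 1.2 both are low: 10–19% against 24–25%.

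**Closed ulcers.** With an offset of 0.05 cm² (the ±5 mm² approximation), a closed ulcer enters as log 0.05 = −3.0; with 0.01 cm² it would enter as −4.6. The ratio of areas therefore depends on the constant. With 19% of ulcers closed, power was 78% for the offset model, 86% for percent reduction and 88% for a rank-based adjusted analysis.

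**The case against.** The strongest reply is that section 2.10 names tests, not variables. A Mann-Whitney test on percent reduction fits its wording, already uses the day-0 area and performs almost as well as the adjusted model. This stands. A reader might infer that the plan tests raw week-6 area or cm² decrease, but no section says so. The documents support only that the variable is undefined and that no adjustment is specified.

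A reader might also infer that chance imbalance in starting area would pass for a treatment effect more often than the nominal level allows. It would not: randomization already accounts for such imbalance in the error rate, and the simulated rates stay near 5%. An imbalance in this particular sample would go uncorrected, which is a matter of precision.

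The 24-fold range of duration (24 ÷ 1 months) and the mix of ischaemic and non-ischaemic stages are tempting additions. The documents give nothing from which to quantify either.

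Finally, wound size is one part of the third outcome, behind the tissue scores and microbiology, and section 2.6 defines complete healing separately. That limits the importance of the point but does not remove it.

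**Conclusion.** The point holds in a limited form. The plan collects the starting area, admits a 30-fold range of it, and specifies neither the wound-size variable nor any use of day-0 area. If week-6 area is tested, power is about 50% down to 30%, against about 92% down to 40% with day-0 area, as individual healing varies from SD 0.6 to 1.2. The gap is about 40 points at the low end of that range and about 10 at the high end. Absolute decrease also loses power, by an amount that depends on average shrinkage. Percent reduction would avoid most of the loss.

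These figures rest on an assumed effect, day-0 distribution and healing SD. The conclusion concerns precision on a third-ranked outcome. It does not show bias, an inflated false-positive rate, or any effect on the main tissue comparison or the stated sample size. It is a change that should be made, not one on which the trial's validity depends.

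**What to change.** In section 2.10, define the wound-size comparison as week-6 area adjusted for day-0 area:

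- Use the post-debridement day-0 reading, which section 2.2 already uses for eligibility, and say so, since section 2.5.3 provides evaluations both before and after debridement.
- Fit a linear model of log area on arm and log day-0 area. Report the ratio of areas with its confidence interval.
- Do not test raw week-6 area or absolute cm² decrease.
- Keep closed ulcers as area 0 with a stated small offset, for example 0.05 cm².
- Because the ratio depends on that offset when many ulcers close, check the result with ranks of week-6 area adjusted for ranks of day-0 area, or with Mann-Whitney on percent reduction.

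The cost is wording, one extra model parameter and one sensitivity analysis. No new measurement or patient is needed. Since the document is dated after recruitment ended, it should also state whether this choice was made before the wound-size results were seen.

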#### 2.6. Follow-Up

Patients were followed up for 6 months after inclusion. During the follow-up period, we recorded ulcer healing. Ulcer healing was defined as complete epithelialization without any sustained drainage up to 24 weeks after the end of the study follow-up.

#### 2.7. Sample Size

Granmov.12 program (Municipal Institute of Medical Research, Barcelona, Spain) (<https://www.imim.cat/ofertadeserveis/software-public/granmo/>) was used to calculate the sample size. Thus, we analyzed 51 patients (24 in surgical group and 27 in UAW group) with a statistical power of 0.80 and an alpha of 0.05, with a

power of the clinical difference of 37% to detect a statistically significant between groups.

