#### 2.4.2. Analysis of Tissue Samples

Soft tissue punch biopsies (3 mm) were taken after wound debridement sessions at week zero (day 0) and week six (day 42). After tissue collection, samples were immediately transported to the laboratory for cellular proliferation and microbiological analyses.

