### 2.5. Outcome Measures

**2.5.1. Main Outcome Measure: Cellular Proliferation Analysis of Wound Tissue Samples.** The same senior clinician interpreted all samples to evaluate the cellular proliferation. The microvascular structure of CD31, an endothelial marker, was subjected to immunohistochemical analysis and quantification to understand the effects of debridement on neo-angiogenesis, [22]. Sections of tissue sample were immunohistochemically stained with the CD31 marker. Light microscopy was used to count the number of microvessels/endothelial cells in a standardized grid, with the results expressed as microvessel density (Leica DMD 800 morphometric system). Microvessel density was scored in proportion to the following scale: 0 (absent), 1 (low, at least one microvessel), 2 (moderate) and 3 (more than two microvessels).

To differentiate collagen content from other components, such as muscle fibrin and erythrocytes, in tissue samples we used Massons's trichome staining. Collagen content was scored according to the following scale: 0 (absent), 1 (mild), 2 (moderate) and 3 (severe) [23].

Actin staining was used to evaluate the presence of myofibroblasts involved in wound healing. These cells increase in number during wound healing. The number of stained cells was semi-quantitatively analyzed using a 0–3 scaling score (0 = no myofibroblasts, 1 = myofibroblasts in low quantities, 2 = myofibroblasts in moderate quantities, 3 = myofibroblasts in high quantities).

**2.5.2. Secondary Outcome Measure: Microbiological Analysis of Wound Tissue Samples** Specimens of wound tissue were homogenized in 0.5 mL volumes of sterile phosphate buffered saline (PBS, Sigma Aldrich, St Louis, MO). After mechanical homogenization, the specimens were seeded in Columbia agar (BD, Sparks, MD), MacConkey agar (BD), Sabouraud dextrose agar (BD) and Columbia

agar supplemented with nalidixic acid and colistin (BD) using a spiral plater Workstation (Don Whitley Scientific, Shipley, UK). Quantitative and qualitative microbiological analyses were performed after incubation of plates at 37 °C for 24 h. Isolated microorganisms were identified by standard methods and susceptibility testing was performed in accordance with Clinical and Laboratory Standards by the disk diffusion method [24]. The results were expressed as CFU per gram of tissue (CFU/g) and the limit of detection was 10 colony-forming units (CFU).

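### The main outcome is three separate 0–3 scores under a single alpha of 0.05, with no lead score, success rule or multiplicity control

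*Combined protocol and SAP*

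**What the plan says.** Section 2.5.1 is headed "Main Outcome Measure: Cellular Proliferation Analysis of Wound Tissue Samples". Under that one heading stand three stains, each with its own 0–3 scale:

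- CD31: "Microvessel density was scored in proportion to the following scale".
- Collagen: "Collagen content was scored according to the following scale".
- Actin (myofibroblasts): "The number of stained cells was semi-quantitatively analyzed using a" 0–3 score.

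No score is named as the lead, no composite is formed, and nothing says whether one, two or all three must differ for the trial to succeed.

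Section 2.7 states: "we analyzed 51 patients (24 in surgical group and 27 in UAW group) with a statistical power of 0.80 and an alpha of 0.05". It adds a "power of the clinical difference of 37% to detect a statistically significant between groups". This is the only significance level in the document. Its sidedness is not given, and the 37% is not tied to any outcome.

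Section 2.10 assigns tests by type of variable: chi-square or Fisher for categorical, t-test or Mann-Whitney for quantitative. It states no significance level, testing order or adjustment, and does not say to which type a 0–3 score belongs. Section 2.4.2 has biopsies at day 0 and day 42, but no section says whether the day-42 score or the change between the two is compared.

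**The concern.** A single alpha describes the risk of a false main conclusion only if a single test, or a stated rule over several tests, leads to that conclusion. Here three tests can be run and the rule that joins them is missing. If a difference on any one score is enough, there are three chances of a false positive. If all three are required, there is no inflation. The document allows both readings, so the 0.05 cannot be attached to the main conclusion.

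The open choices of test and of compared quantity add to the problem, because they leave the three tests themselves undefined.

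**Working it through.** **1. The plan's own figure.** Read the 37% as an absolute difference in proportions (an assumption), two-sided at 0.05, power 0.80, equal arms, no continuity correction:

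n per arm = [z(0.975)·√(2p̄(1−p̄)) + z(0.80)·√(p₁(1−p₁) + p₂(1−p₂))]² / 0.37²

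- p₁ = 0.15, p₂ = 0.52: (1.308 + 0.517)² / 0.1369 = 24.3, so 25 per arm, 50 in total.
- p₁ = 0.20, p₂ = 0.57: 26 per arm, 52 in total.
- Control rates from 0.01 to 0.60: totals from 34 to 56.

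So 51 is attainable but cannot be confirmed, because outcome, control rate and sidedness are missing.

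**2. Inputs for the error rate.**

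- Number of scores: three (section 2.5.1).
- Level per score: 0.05. Section 2.7 gives it as a sample-size input; its use for each test is an assumption.
- Two-sided testing with a directional test: assumed. This gives 0.025 per score favouring UAW.
- Any one score may carry the claim: assumed.
- Correlation ρ between the test statistics: not given, taken as 0, 0.5 and 0.9. Section 2.5.1 has one clinician read all samples, and the scores come from the same biopsies, so a positive value is plausible.

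**3. Formulas.** With no true effect and independent scores:

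- either direction: 1 − 0.95³ = 0.1426
- favouring UAW: 1 − 0.975³ = 0.0731

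For ρ > 0, integrate over a shared standard normal factor x:

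- P(at least one Z > 1.96) = 1 − ∫ Φ((1.96 − √ρ·x)/√(1−ρ))³ φ(x) dx
- For either direction, replace Φ(·) by the probability of lying between −1.96 and 1.96 given x.

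**4. Results.** Under Holm, a first false rejection with no true effect requires p below 0.05/3, so the same integrals apply with 2.394 in place of 1.96.

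| Correlation | Either direction, unadjusted | Favouring UAW, unadjusted | Either direction, Holm | Favouring UAW, Holm |
|---|---|---|---|---|
| 0 | 14.3% | 7.3% | 4.9% | 2.5% |
| 0.5 | 12.5% | 6.3% | 4.5% | 2.2% |
| 0.9 | 8.4% | 4.2% | 3.0% | 1.5% |
| One score only | 5% | 2.5% | – | – |

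The unadjusted rates are about 2.9, 2.5 and 1.7 times the single-score rate. At ρ = 0.95 the rate favouring UAW is 3.7%, and it reaches 2.5% at perfect correlation. Under any dependence it cannot exceed 3 × 2.5% = 7.5%.

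**5. Check with the likely test.** Tie-corrected Mann-Whitney tests were simulated on four-level scores, 24 vs 27, with an assumed spread of 30/40/20/10% over scores 0 to 3 and 60,000 trials. At latent correlations 0, 0.5 and 0.9 the error in either direction was 14.3%, 13.1% and 9.7% unadjusted, and 4.7%, 4.3% and 3.4% with Holm. The values at 0.5 and 0.9 lie above those from the formula because grouping into four levels weakens the correlation: in a separate simulation with two other assumed spreads, a latent 0.9 became 0.81 to 0.84 between the scores.

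**6. Power cost.** For a score with 80% power at 0.05, power at level a is Φ(z(0.975) + z(0.80) − z(1 − a/2)):

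- a = 0.0167: Φ(1.960 + 0.842 − 2.394) = Φ(0.408) = 0.66
- a = 0.025: Φ(1.960 + 0.842 − 2.241) = Φ(0.560) = 0.71

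**The case against.** The strongest reply is that the error rates rest on rules the plan does not contain. It does not say that one score is enough. Section 2.10 sets no level per test, sidedness is unstated, and the correlation is unknown and could exceed 0.9. All of this stands, and it makes the figures conditional. It does not supply the missing rule. If 0.05 were one-sided, the single-score rate favouring UAW would be 5% and the independent case 14.3%, so the inflation would remain. If the scores were treated as categorical, a four-category chi-square has no direction and the favouring-UAW figures would not carry over. Three independent tests that each attain 0.05 would still give 14.3%.

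A second reply is practical: recruitment ended in December 2019 and the document of 20.01.2020 already reports patients as analyzed, so a rule added now cannot be shown to precede the results. That stands too. Disclosure and full reporting are the core of the remedy, and Holm only limits the error.

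Some stronger readings are tempting but not supported:

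- That the trial's false-positive rate *is* 7.3% or 14.3%. This needs the any-one rule and independence, and the document states neither.
- That 51 patients is too few or miscalculated. The total can be reached under plausible inputs (step 1).
- That CD31 adds a further endpoint because it is both counted and scored. The text says "Light microscopy was used to count the number of microvessels/endothelial cells in a standardized grid, with the results expressed as microvessel density" and then scores that density, which reads most naturally as one sequence.
- That the change from day 0 is the tested quantity because section 2.10 mentions a decrease. That word occurs only in the sentence on graphics.

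**Conclusion.** The gap is real and should be fixed. Three scores share one main outcome and the document's only alpha, and nothing says which score or combination decides. If any one score may carry the claim, a false claim favouring UAW is about 1.7 to 2.9 times as likely as with one score. This assumes two-sided directional tests at 0.05 and correlations between 0 and 0.9. The excess shrinks as the correlation approaches 1. Under an all-three rule the error stays at or below 5% in either direction. Confidence is medium: the omission is plain in the text, but its size depends on a rule that the text leaves open.

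**What to change.** In section 2.10:

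- Name one compared quantity for all three scores, either the day-42 score or the change from day 0. Make the other a sensitivity analysis that carries no separate claim.
- State that the 0–3 scores are compared between arms with a tie-corrected Mann-Whitney test.
- Apply Holm across the three at two-sided 0.05: smallest p against 0.0167, next against 0.025, last against 0.05, stopping at the first failure.
- Report all three scores whatever the result.
- Declare that the rule was added after the document of 20.01.2020, so findings on these scores are not prespecified confirmatory evidence.

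In section 2.7, say which outcome and scale the 37% refers to. If it is not one of the three scores, say that the 0.80 does not apply to them. Do not add a detectable effect from a formula that assumes no ties, because a four-level score is heavily tied: with the assumed 30/40/20/10% spread, 0.09 + 0.16 + 0.04 + 0.01 = 30% of between-arm pairs tie when there is no effect.

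The cost is wording only, with no extra patients. A score with 80% power at 0.05 has about 66% at the strictest Holm step and 71% at the second. Holm limits the error but does not restore prespecified status.
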